### 3.7.1 Schedule of Assessments

#### 3.7.1.1 Screening

The screening period begins after written informed consent has been obtained and will take place between Day -28 and Day -1 prior to enrollment. Although the screening period continues up to administration of the first dose of IMP, screening procedures should be initiated with a sufficient amount of time allotted in order to obtain laboratory results and ECG results from the central reader prior to randomization. The sponsor reserves the right to utilize external quality oversight methods to ensure the validity of diagnosis, severity of illness, and other factors determining appropriateness of subject selection. After a subject has been told that a reliable informant may accompany the subject at all visits and signed the ICF or provided assent, a screening number will be provided via eSource. Completion of screening activities may require more than 1 visit; however, only the initial visit will be registered. The screening period maximum of 28 days may be extended after discussion with the medical monitor. Screening evaluations will include the following:

- Trial personnel will enter subject data into eSource to register all trial visits.
- An assessment of all inclusion and exclusion criteria will be made to determine the subject's eligibility for the trial.
- Demographic data will be recorded.
- Medical and psychiatric history will be recorded, including the DSM-5 diagnosis of schizophrenia that will be made by an adequately trained clinician.
- Previous medications taken within 30 days of screening will be recorded. Lifetime antipsychotic use will be recorded. Washout from prohibited concomitant medications will begin, if applicable (see Table 4.1-1).
- Diagnosis of schizophrenia will be confirmed by the K-SADS-PL, performed by an adequately trained rater.
- A qualified and certified rater will administer the PANSS.
- A qualified rater will administer the CGAS.
- The investigator (or qualified designee) will administer the SAS, AIMS, and BARS.
- The investigator (or qualified designee) will administer the UKU and NY-AACENT.

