- Blood samples will be collected for clinical laboratory tests, including hematology and serum chemistry (with blinded prolactin, glycosylated hemoglobin [HbA1c], and thyroid-stimulating hormone [TSH] and free thyroxine [T4]). Blood will be drawn after a minimum 8-hour fast, if fasting is at all possible (see Section 3.7.3.2). See Table 3.4.3-1 for exclusions based on outcome of screening clinical laboratory tests. Vital sign and ECG assessments should be completed before any blood samples are collected.
- A serum pregnancy test will be performed for all females. Subjects with a positive serum test result will be excluded from the trial.
- Urine will be collected from all potential subjects for urinalysis and urine screen(s) for drugs of abuse. See Table 3.4.3-1 for exclusions based on outcome of urine drug screen(s). A urine pregnancy test will be performed for all females.
- AEs and concomitant medications will be recorded beginning with the signing of the ICF.

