If a subject is experiencing an EPS, the specific EPS must be indicated on the AE screen in eSource. Examples of AEs that are considered EPS include, but are not limited to: generalized rigidity, hyperkinesia, bradykinesia, akinesia, dystonia, hypertonia, akathisia, tremor, flexed posture, involuntary muscle contractions, athetosis, and chorea. If a subject is experiencing 2 or more of these symptoms, whether or not treatment with an anticholinergic is required, this is considered as extrapyramidal syndrome and must be entered as "extrapyramidal syndrome" on the AE screen in eSource instead of the individual symptoms. Permitted treatments for EPS are described in Section 4.2.1.

Immediately Reportable Event (IRE):

- Any SAE.
- Any AE related to occupational exposure.
- Potential serious hepatotoxicity cases (any increase of AST or ALT ≥ 3 times the upper normal limit or screening value with an increase in total bilirubin ≥ 2 times the upper normal limit or screening value)
- Pregnancies are also defined as IREs. Although normal pregnancy is not an AE, it will mandate IMP discontinuation and must be reported on an IRE form to the sponsor. Pregnancy will only be documented on the AE screen in eSource if there is an abnormality or complication.

Clinical Laboratory Test Value Changes: It is the investigator's responsibility to review the results of all laboratory tests as they become available. This review will be documented by the investigator's dated signature on the laboratory report. For each abnormal laboratory test result, the investigator needs to ascertain if this is an abnormal (ie, clinically significant) change from baseline for that individual subject. This determination, however, does not necessarily need to be made the first time an abnormal value is observed. The investigator may repeat the laboratory test or request additional tests to verify the results of the original laboratory tests. If this laboratory value is considered medically relevant by the investigator (subject is symptomatic, requiring corrective treatment or further evaluation), or if the laboratory value leads to discontinuation, or fulfills a seriousness criterion, this is considered an AE.

Severity: Adverse events will be graded on a 3-point scale and reported as indicated in eSource. The intensity of an adverse experience is defined as follows:

- **1 = Mild:** Discomfort noticed, but no disruption to daily activity.

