# 5.2 Eliciting and Reporting Adverse Events

The investigator will periodically assess subjects for the occurrence of AEs. To avoid bias in eliciting AEs, subjects should be asked the non-leading question: "How have you felt since your last visit?" All AEs (serious and nonserious) reported by the subject must be recorded on the source documents and in eSource provided by the sponsor. The AE collection is to begin after a subject has signed the ICF.

Use medical terminology in AE reporting. Adverse events should be reported as a single unifying diagnosis whenever possible or, in the absence of a unifying diagnosis, as individual signs or symptoms. Exacerbation or disease progression should be reported as an AE only if there are unusual or severe clinical features that were not present, or experienced earlier, or not expected based on the course of the condition. A reported AE that undergoes a change in severity, seriousness, or toxicity should be reported as a new AE in eSource.

Note: Normal pregnancy is not an AE and should not be recorded as one in eSource; guidelines outlined in Section 5.5 should be followed for pregnancy reporting.

In addition, the sponsor must be notified immediately by telephone, fax, or e-mail of any IREs according to the procedure outlined below, in Section 5.3. Special attention should be paid to recording hospitalization and concomitant medications.

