The start date of double-blind IMP with brexpiprazole, aripiprazole or placebo will be the first day of double-blind dosing. The number and percentage of subjects who receive double-blind IMP will be presented by week and by treatment group. Each dosing week will be based on the actual week; ie, Day 1 to 7 in Week 1, Day 8 to 14 in Week 2, etc. This summary will be performed on the Safety Sample.

The number and percentage of completers will be presented by week and by treatment group.

The mean daily dosage will be summarized by week and treatment group using descriptive statistics. The mean daily dosage per subject per week will be determined for each week of the trial. This will be calculated by dividing the sum of individual total doses by the number of days in the week interval. The summary will contain for each treatment group the number of subjects receiving double-blind IMP, and the mean and range of the mean daily dose for each week.

Extent of exposure will also be summarized by sex, race (White and All Other races), age category (< $15, \ge 15$ years) and region (US, Europe [continent], Mexico).

9

All AEs will be coded by system organ class and Medical Dictionary for Regulatory Activities (MedDRA) preferred term. The incidence of the following events will be summarized by treatment group:

- 1) Treatment-emergent AEs (TEAEs),
- 2) TEAEs by severity
- 3) TEAEs potentially causally related to the IMP,
- 4) TEAEs potentially causally related to the IMP by severity,
- 5) TEAEs with an outcome of death,
- 6) Serious TEAEs,
- 7) TEAEs leading to discontinuations of the IMP.

Treatment-emergent AE is defined as an AE that started after trial drug treatment, or if the event was continuing from baseline and was serious, trial drug related, or resulted in death, discontinuation, interruption or reduction of trial therapy.

Incidence of TEAEs will also be summarized by sex, race (White and All Other races), age category (< 15, \geq 15 years) and region (US European [continent], Mexico).

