9.10 Other Safety Data

Incidence of Onset of Akathisia Adverse Event by Week will be presented.

Incidence of sign/symptom items as recorded in the NY-AACENT scale will be summarized. Specifically, incidence (and severity) of the sign/symptom items will be tabulated by study visit, based on the OC data. The summarization will be repeated for the subset of drug-related signs or symptoms and for the subset of function impaired signs or symptoms, respectively. Additionally, change from baseline in the NYAACENT total score will be summarized on the OC data by study visit and on the LOCF data for the last assessment visit.

The UKU, NY-AACENT scale will also be summarized by week using the OC datasets of the Safety Sample.

The summary of Tanner Scale for OC datasets of the Safety Sample will be provided for week 6 and shift from baseline. The collection of Tanner Staging data is required for this trial, and every attempt will be made to collect this information. Tanner Staging will be completed together with the physical examination. When Tanner Staging is not completed at a required visit, it will be collected at the next trial visit. A subject who reaches Stage 5 (both in pubic hair and genitalia) does not need to continue with Tanner Staging.

The incidence of the individual side effects and categories of side effects recorded in the UKU will be summarized by treatment group for the Safety Sample by severity and causal relationship. In addition, the global assessment of side effects and the measures taken on the basis of the side effects will be summarized by incidence in a similar fashion to the above.

10 Scales: Rules for Scoring and Handling of Missing Data

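### Recording every change of severity as a new AE lets a washout symptom that merely eases after the first dose count as treatment-emergent

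*Protocol*

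**What the plan says.** Protocol 5.2 (Eliciting and Reporting Adverse Events) sets the recording rule: "A reported AE that undergoes a change in severity, seriousness, or toxicity should be reported as a new AE in eSource". The sentence does not restrict the change to worsening. Protocol 5.1 supplies the grades: "Adverse events will be graded on a 3-point scale and reported as indicated in eSource", namely mild, moderate and severe.

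Collection starts before treatment. Protocol 5.2 states "The AE collection is to begin after a subject has signed the ICF", and Protocol 3.7.1.1 (Screening) repeats "AEs and concomitant medications will be recorded beginning with the signing of the ICF". Washout of prohibited medication takes place in the same screening period of up to 28 days. Table 4.1-1 allows oral benzodiazepine rescue during washout, and its footnote names agitation and insomnia as the reasons.

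SAP 9.2 (Adverse Events) has two limbs. The first is unconditional: "Treatment-emergent AE is defined as an AE that started after trial drug treatment". The second is conditional: or "if the event was continuing from baseline and was serious, trial drug related, or resulted in death, discontinuation, interruption or reduction of trial therapy". TEAE incidence is then tabulated by treatment group, overall and by severity. Protocol 7.6.1 lists the TEAE tables without defining the term. SAP 9.10 adds one timing table: "Incidence of Onset of Akathisia Adverse Event by Week will be presented".

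Neither document links split records, compares a post-dose grade with the pre-dose grade, or excludes improvement. The SAP addendum of 21 August 2023 adds TEAE tables by race and ethnicity and leaves the methods unchanged.

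**The concern.** The second limb of the SAP definition is a filter. A symptom already present at baseline should count only if it is serious, related to trial drug, or has one of the listed consequences for the subject or the treatment. The Protocol 5.2 rule can bypass that filter. Suppose insomnia is moderate on Day -5 and mild from Day 3. Under Protocol 5.2 it becomes a new AE, mild. If that record starts on Day 3, it falls under the first limb, which sets no condition, and the subject has a TEAE of insomnia because the insomnia improved.

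At stake is how individual terms read in the adolescent safety tables. Eased washout symptoms would add to the incidence in all three arms, placebo included, and so blur the contrast for the terms most likely to appear during withdrawal of earlier medication. The primary efficacy analysis is not touched.

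**Working it through.** **1. Which limb applies.** Take a nonserious, unrelated pre-dose AE that leads to no action on treatment.

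| Course after first dose | Kept as one record | New record starting on date of change |
|---|---|---|
| Eases by one grade | Second limb: not a TEAE | First limb: TEAE |
| Worsens by one grade | Second limb: not a TEAE | First limb: TEAE |

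The top row is the defect. The bottom row is why the rule cannot simply be deleted: the SAP has no general limb for worsening from baseline, so splitting the record is what captures ordinary worsening.

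**2. Size.** The plan states no TEAE rate for this trial, so there is no figure to reproduce. Inputs:
- p, the incidence of genuine TEAEs of a term. As illustrations: insomnia 8.1% and any TEAE 69.1%, the pooled brexpiprazole rates in Protocol 1.3. These are reported rates from other trials.
- p0 = 5% for insomnia on placebo: an assumption.
- q, the share of subjects whose ongoing pre-dose AE of that term eases after the first dose: an assumption, shown from 0 to 16% and taken as independent of p.

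Observed subject-level incidence = p + (1 - p)q. For insomnia at q = 5%: 0.081 + 0.919 × 0.05 = 0.127.

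With equal q in both arms, the observed risk difference is [p + (1 - p)q] - [p0 + (1 - p0)q] = (p - p0)(1 - q).

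| q (assumed) | Insomnia, drug | Insomnia, placebo | Difference, points | Ratio | Any TEAE, drug |
|---|---|---|---|---|---|
| 0 | 8.1% | 5.0% | 3.100 | 1.62 | 69.1% |
| 1% | 9.02% | 5.95% | 3.069 | 1.52 | 69.4% |
| 2% | 9.94% | 6.90% | 3.038 | 1.44 | 69.7% |
| 5% | 12.70% | 9.75% | 2.945 | 1.30 | 70.6% |
| 10% | 17.29% | 14.50% | 2.790 | 1.19 | 72.2% |
| 16% | 22.80% | 20.20% | 2.604 | 1.13 | 74.0% |

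Per 105 subjects, q = 5% adds 105 × 0.919 × 0.05 = 4.8 subjects with insomnia, and 105 × 0.309 × 0.05 = 1.6 with any TEAE. For any TEAE the relevant q runs over all terms, so it is at least as large as for one term.

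**3. Unequal shares.** Easing happens after randomisation, so q may differ by arm. The difference is then (p - p0) + (1 - p)q1 - (1 - p0)q0, where q1 is the drug share and q0 the placebo share. With q1 = 5% and q0 = 2% (assumed) it is 12.695 - 6.900 = 5.8 points. With the shares reversed it is 9.938 - 9.750 = 0.2 points. The bias can go either way, and the documents support neither case.

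**4. Splitting within treatment.** Akathisia that starts on treatment and goes mild, moderate, mild yields three records but one subject, so subject-level incidence does not change. The akathisia onset-by-week table is exposed only because the SAP does not say whether a subject counts once.

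**The case against.** The strongest reply is that the text does not go this far. Protocol 5.2 uses advisory wording and never mentions improvement. Neither document says which start date the new record carries; if completion instructions keep the original onset, the second limb applies and the eased symptom is excluded. This stands as a limit on certainty. It does not remove the problem, because a new AE most naturally starts when the change occurs and no text in either document prevents that reading.

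The pool of affected records is also narrower than all washout complaints. Symptoms that predate consent may be medical history, and expected disease exacerbation is largely not reportable as an AE under Protocol 5.2. That also stands.

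Three stronger inferences are tempting, and the documents do not support them:
- **The drug-placebo comparison is badly distorted.** A ratio as low as 1.13 needs an assumed 16% share and an assumed placebo rate. At that same share the difference moves only from 3.1 to 2.6 points.
- **Every AE table is affected.** A nonserious symptom that eases does not enter the serious or discontinuation tables. It enters the related-TEAE table only if the investigator judges it related to trial drug, which is not to be expected of a fading washout symptom.
- **On-treatment splitting multiplies TEAE rates or all onset counts.** The SAP tabulates incidence, usually meaning subjects, and plans onset by week for akathisia alone.

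**Conclusion.** The concern holds as a defect in how the two documents work together. Followed as written, Protocol 5.2 moves an easing baseline symptom out of the SAP's conditional limb and into its unconditional one. This rests on the new record starting on the date of change.

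The direction is certain for any affected share above zero: subject-level incidence of the term rises by (1 - p)q in each arm. With equal shares the risk ratio moves toward 1, while the risk difference shrinks only by the factor (1 - q). Any-TEAE incidence changes little: 69.1% to 70.6% at an assumed 5%, 72.2% at 10%. The actual size is unknown because the documents do not give the share. The point is worth correcting before the safety tables are read term by term, but it is not a threat to the trial's main conclusion.

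**What to change.** Make the main change in SAP 9.2, because the SAP's section on the Ukraine-Russia conflict (8.1.5) already describes enrolment in the past tense and a SAP rule also repairs data already recorded.

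- **Linking.** Join a post-dose record to a pre-dose AE of the same preferred term when the two are contiguous, that is, when the earlier end date equals or adjoins the later start date.
- **Counting.** Count the linked record as treatment-emergent only if its severity exceeds the worst pre-dose severity, or if it meets any criterion already in the second limb. Keep all of these: seriousness, relation to trial drug, and an outcome of death or of stopping, interrupting or reducing trial therapy.
- **Recurrence.** An event that returns after a resolved gap stays a new TEAE.
- **SAP 9.10.** Count each subject once, at the first treatment-emergent akathisia onset.
- **Protocol 5.2, only if it is amended again.** Limit new entries to worsening severity or newly met seriousness, and record improvement on the existing AE. An amendment made for this alone would leave AEs recorded in two ways within one trial.

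The cost is a small amount of programming and dependence on accurate AE end dates; onset date, severity and preferred term alone cannot separate a continuation from a recurrence. Comparing with the worst pre-dose grade also means that a return to a grade already reached before dosing is not counted, which the SAP should state.

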#### 5.3 Immediately Reportable Events

The investigator must immediately report after either the investigator or site personnel become aware of any SAE, serious hepatotoxicity, or confirmed pregnancy, by telephone, fax, or e-mail to the sponsor using the contact information on the cover page of this protocol. An IRE form must be completed and sent by e-mail, fax, or overnight courier to the sponsor. (Please note that the IRE form is NOT the AE screen in eSource.)

Subjects experiencing SAEs should be followed clinically until their health has returned to baseline status, or until all parameters have returned to normal or have otherwise been explained. It is expected that the investigator will provide or arrange appropriate

supportive care for the subject and will provide prompt updates on the subject's status to the sponsor.

#### 5.4 Potential Serious Hepatotoxicity

For a subject who experiences an elevation in AST or ALT that is  $\geq 3$  times the ULN, a total bilirubin level should also be evaluated. If the total bilirubin is  $\geq 2$  times the ULN, complete an IRE form with all values listed and also report as an AE in eSource.

#### 5.5 Pregnancy

For females and for men who are sexually active, there must be a documented agreement that the subject or their partner will take effective measures (ie, double-barrier method) to prevent pregnancy during the course of the trial and for 30 days after the last dose of IMP. Unless the subject is sterile (ie, females who have had a bilateral oophorectomy or hysterectomy or who have been postmenopausal for at least 12 consecutive months; or men who have had a bilateral orchidectomy) or remains abstinent, 2 of the following precautions must be used: vasectomy, tubal ligation, vaginal diaphragm, intrauterine device, birth control pills, birth control depot injection, birth control implant, birth control patch, condom with spermicide, or sponge with spermicide. Any single method of birth control, including vasectomy and tubal ligation, may fail, leading to pregnancy. The contraceptive method will be documented at each trial visit.

Before enrolling females in this clinical trial, investigators must review the below guidelines about trial participation with all females. The topics should generally include:

- General information
- Informed consent form
- Pregnancy prevention information
- Drug interactions with hormonal contraceptives
- Contraceptives in current use
- Guidelines for the follow up of a reported pregnancy

Before trial enrollment, females must be advised of the importance of avoiding pregnancy during trial participation and the potential risk factors for an unintentional pregnancy. The subject must provide assent or e-sign the electronic ICF stating that the above-mentioned risk factors and the consequences were discussed with her.

A urine or serum pregnancy test for human chorionic gonadotropin will be performed at screening on all female subjects. At any time during the trial if a urine test is performed and is positive, the investigator will follow up with a confirmatory serum test.

During the trial, all females should be instructed to contact the investigator immediately if they suspect they might be pregnant (eg, missed or late menstrual cycle).

If a subject is suspected to be pregnant before she receives IMP, the IMP administration must be withheld until the results of serum pregnancy tests are available. If the pregnancy is confirmed, the subject must not receive the IMP and must not be enrolled in the trial. If pregnancy is suspected while the subject is taking IMP, the IMP must be withheld immediately (if reasonable, taking into consideration any potential withdrawal risks) until the result of the pregnancy test is known. If pregnancy is confirmed, the IMP will be permanently discontinued in an appropriate manner (eg, dose tapering if necessary for subject safety) and the subject will be withdrawn from the trial. Exceptions to trial discontinuation may be considered for life-threatening conditions only after consultations with the Clinical Safety and Pharmacovigilance department (see the cover page of this protocol for contact information).

The investigator must immediately notify the sponsor of any pregnancy associated with IMP exposure during the trial and for 30 days after the last dose of IMP and record the event on the IRE form and forward it to the sponsor. The sponsor will forward Pregnancy Surveillance Form(s) for monitoring the outcome of the pregnancy.

Protocol-required procedures for trial discontinuation and follow up must be performed on the subject unless contraindicated by pregnancy (eg, x-ray studies). Other appropriate pregnancy follow-up procedures should be considered, if indicated. In addition, the investigator must report to the sponsor, on appropriate Pregnancy Surveillance Form(s), follow-up information regarding the course of the pregnancy, including perinatal and neonatal outcome. Infants will be followed for a minimum of 6 months from the date of birth. Local regulatory requirements must be followed for follow up and reporting on pregnancy cases or infants.

